### **2.1.13. Mortality**

In Africa trial, as a partner drug with amphotericin B, flucytosine was superior to fluconazole (71 deaths [31.1%] vs. 101 deaths [45.0%]; hazard ratio for death at 10 weeks, 0.62; 95% confidence interval [CI], 0.45 to 0.84;  $P = 0.002$ ). One week of amphotericin B plus flucytosine was associated with the lowest 10-week mortality (24.2%; 95% CI, 16.2 to 32.1) (Molloy et al., 2018).

In Thailand study, the standard therapy for human immunodeficiency virus (HIV)-associated cryptococcal meningitis of amphotericin B (AmB; 0.7 mg/kg per day) plus flucytosine frequently takes 12 weeks to sterilize the cerebral spinal fluid, and acute mortality remains high. In this trial of AmB-based combination therapy, the 10-week survival rate was 76%, the highest reported to date from Africa (Bicanic et al., 2008) At least two factors might explain high acute mortality: raised intracranial pressure and only moderately effective antifungal regimens, which frequently take more than 2 weeks to sterilize CSF. Mortality was 14% (nine/63) at 2 weeks and 22% (14/63) at 10 weeks. Elevated intracranial pressure was associated with death in 13 of 14 patients during step one. For the initial treatment of AIDS associated cryptococcal meningitis, the use of higher-dose amphotericin B plus flucytosine is associated with an increased rate of cerebrospinal fluid sterilization and decreased mortality at two weeks, as compared with regimens used in previous studies (Van Der Horst et al., 1997). In Vietnam study, combination therapy with flucytosine was associated with a reduced hazard of death, as compared with amphotericin B alone (hazard ratio, 0.56; 95% CI, 0.36 to 0.87;  $P = 0.01$ ) or with amphotericin B plus fluconazole (hazard ratio, 0.55; 95% CI, 0.35 to 0.88;  $P = 0.01$ ) (Day et al., 2013).

### **2.2.14. Timing of ART**

Immediate ART initiation is not recommended for adults, adolescents and children living with HIV who have cryptococcal meningitis because of the risk of increased mortality and should be deferred by 4–6 weeks from the initiation of antifungal treatment (WHO, 2018).

### **3. AIM AND OBJECTIVES**

#### **3.1. Aim**

To study the clinical effectiveness and safety of amphotericin B with flucytosine-fluconazole therapy for cryptococcal meningitis in patients with HIV infection.

#### **3.2. Objectives**

1. To find out the back-ground characteristics of patients with HIV-associated cryptococcal meningitis
2. To describe the clinical effectiveness of amphotericin B with flucytosine-fluconazole combination therapy by assessing clinical parameters at day 1, day 7 and day 14
3. To determine the severity of headache before and after treatment by numerical rating scale
4. To describe the clinical safety of amphotericin B with flucytosine-fluconazole combination therapy by assessing hematological and biochemical parameters by DAIDS grading at baseline, day 7 and day 14

#### **3.3. Research Question**

What will be the clinical effectiveness and safety of Amphotericin B with Flucytosine -Fluconazole combination therapy for cryptococcal meningitis in patients with HIV infection?

## **4. METHODOLOGY**

### **4.1. Study Design**

Hospital-based descriptive study

### **4.2. Study Site**

1. Inpatient Departments of Specialist Hospital Waibargi (SHW)
2. Inpatient Departments of Specialist Hospital Mingalardon (SHM)
3. Inpatient Departments of Specialist Hospital Thakeyta (SHT)

### **4.3. Study Period**

This study period will be conducted from October 2020 to September 2021.

### **4.4. Reference Population**

Cryptococcal meningitis in patients with HIV infection

### **4.5. Study Population**

Patients admitted to SHW, SHM and SHT with HIV-associated cryptococcal meningitis who will be treated with amphotericin + flucytosine + fluconazole induction regimen.

### **4.6. Selection Criteria**

#### **4.6.1. Inclusion criteria**

1. Patients with HIV-associated cryptococcal meningitis, admitted to inpatient department of SHW, SHM and SHT during the study period
2. Patients of both sexes
3. Age above 14 years
4. Patients or caregivers who will give informed consent to participate in this study

#### **4.6.2. Exclusion criteria**

1. Pregnancy

#### **4.6.3 Withdrawal criteria**

1. On patient's request

#### **4.7. Sample Size Determination and Sampling Procedure**

##### **4.7.1. Sample Size Determination**

The sample size was calculated by using the following formula

$$z_{(1-\frac{\alpha}{2})}^2 p (1-p)$$

$$n = \frac{z_{(1-\frac{\alpha}{2})}^2 p (1-p)}{d^2}$$

Sample size for clinical safety,

Where,

p = Proportion of absence of grade III/IV anaemia in patients with HIV-associated cryptococcal meningitis infection after being treated with Amphotericin B, Flucytosine plus Fluconazole  
= 0.83 (Molloy et al., 2018)

z = Standard normal deviate = 1.96 (95% CI)

d = Absolute precision = 0.14

n = minimal required sample size = 27

Sample size for clinical effectiveness,

Where,

p = Proportion of improvement of headache in patients with HIV-associated cryptococcal meningitis infection after being treated with Amphotericin, Flucytosine plus Fluconazole  
= 0.8

z = Standard normal deviate = 1.96 (95% CI)

d = Absolute precision = 0.15

n = minimal required sample size = 27

So, the required sample size is 27.

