### **2.1.12. Safety**

In ACTA trial, they randomly assigned HIV-infected adults with cryptococcal meningitis to receive an oral regimen (fluconazole [1200 mg per day] plus

flucytosine [100 mg per kilogram of body weight per day] for 2 weeks), 1 week of amphotericin B (1 mg per kilogram per day), or 2 weeks of amphotericin B (1 mg per kilogram per day). Each patient assigned to receive amphotericin B was also randomly assigned to receive fluconazole or flucytosine as a partner drug. Laboratory-defined side effects were less frequent in the oral-regimen group than in the 1-week or 2-week amphotericin B groups. Grade 4 anemia developed in 0.9% of patients in the oral-regimen group, 4.9% of patients in 1-week amphotericin B groups, and 8.8% of patients in the 2-week amphotericin B group. And also Grade 3 anemia developed in 4% of patients in the oral-regimen group, 8.9% of patients in 1-week amphotericin B groups, and 17.5% of patients in the 2-week amphotericin B group. A grade 3 or 4 increase in the serum creatinine level developed in 4.9% of patients in the oral-regimen group, 6.2% of patients in the 1-week amphotericin B groups, and 8.8% of patients in the 2-week amphotericin B groups. Grade 4 hypokalemia developed in only one patient, most likely because preemptive electrolyte replacement was provided for patients receiving amphotericin B.

Grade 4 neutropenia was recorded in 3.2% of the patients who were taking a regimen that included 2 weeks of flucytosine, in 0.9% of those taking 1 week of flucytosine, and in 1.3% of those taking a flucytosine free regimen. A grade 4 increase in the alanine aminotransferase level developed in only two patients, one of whom was taking fluconazole. Clinical adverse events were frequent with all regimens, which was reflective of the severe immunosuppression in this patient population.

As a partner drug with amphotericin, 1week amphotericin and flucytosine group develop Grade 3 and 4 anaemia of 8.8% and 24.56 % in 2 weeks amphotericin and fluconazole group. (Molloy et al., 2018).

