#### **4.7.2 Sampling Method**

All patients admitted to the inpatient departments of SHW, SHM and SHT during the study period will be included.

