#### **4.8. Materials and Methods**

After getting approval from medical superintendent, patients with HIV-associated cryptococcal meningitis admitted to inpatient departments of SHW, SHM and SHT will be studied. They will be given IV infusion of amphotericin B (1 mg/kg/day) and oral flucytosine (100 mg/kg) for one week followed by oral fluconazole (1200 mg/day) for one week according to the hospital standard treatment guideline chosen by the physician depends on patient's clinical condition. Before giving treatment, informed consent will be obtained.

All patients meeting the inclusion criteria will be studied under the supervision of experienced physicians. Baseline data for assessing clinical effectiveness such as fever, convulsion and abnormal mental status and for safety such as hematological and biochemical parameters (hemoglobin, neutrophil, platelet, ALT, AST, serum creatinine and serum potassium level) will be noted from medical charts. Hematological and biochemical parameters will be graded according to DAIDS grading. Assessment of headache and its severity will be done by numerical rating scale under the supervision of physician.

Seven days and fourteen days after treatment, clinical effectiveness parameters such as headache, fever, convulsion, abnormal mental status and death will be reassessed. Clinical safety concerning hematological and biochemical parameters like hemoglobin, neutrophil, platelet, ALT, AST, serum creatinine and serum potassium level will also be reassessed and graded according to DAIDS grading by reviewing from patient's medical charts at seven and fourteen days. With regard to severity of headache, it will be documented by using numerical rating scale at weekly intervals for two weeks. Clinical effectiveness parameters (headache, fever, convulsion, abnormal mental status and death) and hematological and biochemical parameters will be described. The results will be documented for data analysis.

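### The safety p = 0.83 does not match any grade 3/4 anaemia rate that the protocol quotes from the trial it credits, and both calculations are rounded down to 27 where 28 is the smallest n that meets the stated precision

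*Combined protocol and SAP*

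**What the plan says.** Protocol section 4.7.1 uses the single-proportion precision formula with z = 1.96, once for safety and once for effectiveness.

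- **Safety.** p is defined as "Proportion of absence of grade III/IV anaemia in patients with HIV-associated cryptococcal meningitis infection after being treated with Amphotericin B, Flucytosine plus Fluconazole". It is set at 0.83 and credited to the African (ACTA) trial. With d = 0.14 the minimum n is given as 27.
- **Effectiveness.** p is the proportion whose headache improves. It is set at 0.8 with no source. With d = 0.15 the minimum n is again 27.
- **Overall.** "So, the required sample size is 27".

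Section 2.1.12 reports anaemia from the same trial. By arm: "1week amphotericin and flucytosine group develop Grade 3 and 4 anaemia of 8.8% and 24.56 % in 2 weeks amphotericin and fluconazole group". By pooled duration, for the milder of the two grades: "Grade 3 anemia developed in 4% of patients in the oral-regimen group, 8.9% of patients in 1-week amphotericin B groups, and 17.5% of patients"; here the last figure belongs to the groups treated for two weeks. For the more severe grade, the text reads: "Grade 4 anemia developed in 0.9% of patients in the oral-regimen group, 4.9% of patients in 1-week amphotericin B groups, and 8.8% of patients"; again the last figure is the two-week one.

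Section 4.8 gives the study regimen as one week of amphotericin B with "oral flucytosine (100 mg/kg) for one week followed by oral fluconazole (1200 mg/day) for one week". Section 4.7.2 adds that "All patients admitted to the inpatient departments of SHW, SHM and SHT during the study period will be included". Section 4.9 plans numbers and percentages only. Table 10 shows grade 3 and 4 anaemia at baseline, day 7 and day 14.

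**The concern.** The study is descriptive, with no comparator and no hypothesis test, so p and d are the whole justification for n. The safety p implies 17% grade 3/4 anaemia. That is about 1.9 times the 8.8% quoted from the credited trial for the same induction week (17/8.8 = 1.93), and about 1.2 times the pooled 13.8% (17/13.8 = 1.23). The reader is left with more than one expected anaemia rate from a single citation, and the observed rate will naturally be read against it.

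The second matter is rounding. An n presented as a minimum for a given precision should deliver that precision, and 27 does not quite do so in either calculation.

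**Working it through.** **Inputs.** From 4.7.1: z = 1.96; safety p = 0.83, d = 0.14; effectiveness p = 0.8, d = 0.15. From 2.1.12: the anaemia rates quoted above.

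**Step 1: the plan's own figure.** n = z² p(1 − p)/d².

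- Safety: 3.8416 × 0.83 × 0.17 / 0.0196 = 27.66
- Effectiveness: 3.8416 × 0.80 × 0.20 / 0.0225 = 27.32

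Both become 27 only if the fraction is dropped. Rounded up, both are 28.

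**Step 2: precision delivered.** Half-width = 1.96 √(p(1 − p)/n).

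- n = 27: 0.1417 for safety (stated 0.14) and 0.1509 for effectiveness (stated 0.15)
- n = 28: 0.1391 and 0.1482

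The shortfall at 27 is 0.0017 and 0.0009. The smallest n that meets both targets is 28.

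**Step 3: does any quoted rate give 0.83?** Grade 3 plus grade 4 anaemia in 2.1.12, and its complement:

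| Group | Grade 3/4 anaemia | p (free of it) |
|---|---|---|
| African trial, 1 week amphotericin B + flucytosine | 8.8% | 0.912 |
| African trial, pooled 1-week groups | 8.9 + 4.9 = 13.8% | 0.862 |
| African trial, 2 weeks amphotericin B + fluconazole | 24.56% | 0.754 |
| African trial, pooled 2-week groups | 17.5 + 8.8 = 26.3% | 0.737 |
| African trial, oral regimen | 4 + 0.9 = 4.9% | 0.951 |
| Vietnam trial, amphotericin B + flucytosine | 35% | 0.65 |
| Vietnam trial, amphotericin B + fluconazole | 29% | 0.71 |

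The cohort of amphotericin B with fluconazole is quoted as having no grade 3 or 4 anaemia. None of these gives 0.83. Adding the two grades assumes that each patient is counted once, at the worst grade, which 2.1.12 does not state.

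**Step 4: what the choice changes.** The rates from the credited trial that relate to one week of amphotericin B, beside the plan's value, at d = 0.14:

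| p | n before rounding | n rounded up | Half-width, n = 27 | Half-width, n = 28 | Expected events, n = 28 |
|---|---|---|---|---|---|
| 0.83 | 27.66 | 28 | 0.142 | 0.139 | 28 × 0.17 = 4.8 |
| 0.862 | 23.31 | 24 | 0.130 | 0.128 | 28 × 0.138 = 3.9 |
| 0.912 | 15.73 | 16 | 0.107 | 0.105 | 28 × 0.088 = 2.5 |

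Effectiveness needs 28 whichever row is right. It therefore equals the safety n at 0.83, exceeds it at the other two values, and gives an overall n of 28 each time.

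**The case against.** The strongest reply is that nothing in the conduct of the study turns on this. To two decimals, the half-widths at n = 27 are 0.14 and 0.15, exactly as stated. The gap is one patient, 27 is only a minimum, and every eligible admission is to be taken. Both alternative values need fewer patients for safety than 0.83, so the present input errs on the cautious side. All of that stands and limits the weight of the point. It does not make 27.66 round to 27, and it does not reconcile the two sections.

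A second reply is that 0.83 may be a legitimate count from the trial report. The definition in 4.7.1 includes follow-on fluconazole, whereas the 8.8% is quoted without any mention of it and without a time window. This also stands. A reader might infer that 0.83 is wrong and 0.912 right, but the documents show a mismatch and not which figure is in error. The 8.8% and 13.8% do not contradict each other either: if the two 1-week arms were of equal size (an assumption), the other arm would be at 2 × 13.8 − 8.8 = 18.8%.

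A reader might also try to trace 0.83 to another percentage in 2.1.12. The nearest is the complement of 17.5%, which is 0.825, but as quoted that is grade 3 alone after two weeks of amphotericin B, and nothing says that it was used. Likewise, 8.8% might be taken for a copying slip because it also appears for other quantities, such as creatinine ("6.2% of patients in the 1-week amphotericin B groups, and 8.8% of patients in the 2-week amphotericin B groups"). No derivation is given, and repetition alone does not show a slip, so neither guess is supported.

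**Conclusion.** The point holds in two limited parts. First, the safety p of 0.83 disagrees with the grade 3/4 anaemia rates that the protocol itself quotes from the trial it credits, and its derivation is not given. Second, both sample sizes are rounded down, and the stated precision is narrowly missed at 27.

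The size is small: one patient, and less than 0.002 in half-width. The safety requirement is 28, 24 or 16 depending on the confirmed value, and the overall n is 28 in each case. A reader might infer that the study is too small or must recruit more. The documents do not support that, because the quoted alternatives for one week of amphotericin B in the credited trial lower the safety requirement and 4.7.2 sets no cap.

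Confidence is high on the mismatch and the rounding. Which rate is correct cannot be settled without the cited report. The overall n of 28 rests on the effectiveness p of 0.8, for which 4.7.1 gives no source.

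**What to change.** 1. Check 2.1.12 and 4.7.1 against the cited trial report and make them agree.
2. In 4.7.1, state the arm, the grades and the time window behind p.
3. Restate the safety n, rounded up, for the confirmed value: 28 at 0.83, 24 at 0.862, 16 at 0.912.
4. Restate the effectiveness n and the overall n as 28. Give a source for p = 0.8 or label it an assumption.
5. State the expected safety half-width at n = 28: 13.9, 12.8 or 10.5 percentage points respectively.

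Optional and separate from the arithmetic: because n is set by the precision of a 95% interval, report the grade 3/4 anaemia proportion in 4.9 and Table 10 with a Wilson or exact 95% interval. With two to five events expected, the exact interval would be 0.9% to 23.5% for 2/28, 4.0% to 32.7% for 4/28 and 6.1% to 36.9% for 5/28.

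The cost is one paragraph in 4.7.1, a figure in 2.1.12 if that proves to be the wrong one, and, for the optional item, one sentence in 4.9 and an interval in Table 10. No patients or procedures are added. If a value other than 0.83 is confirmed, 4.7.1 must say that effectiveness alone sets n.

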#### **4.9. Data Management and Analysis**

Data will be collected by using pre-constructed pro forma. Following data collection and prior to data entry, all data will be carefully screened for accuracy.

Data entry will be done by using Microsoft Excel 2019. The data will be statistically analyzed by using computerized statistical software SPSS (Statistical Package for Social Science Version 21).

Data summarization for description will be done by showing frequency distribution tables and appropriate graphs. The parameters for clinical effectiveness and laboratory-defined adverse event gradings will be described by number, percentage in treatment group.

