###### **(i) Severity of headache**

Severity of headache is assessed by using Numerical rating scale (NRS). The NRS score range from zero to 10. Headache severity will be categorized according to the number given by patients for their headache. Headache will be categorized as no pain, mild, moderate, severe, and intolerable when scores are 0, 1-3, 4-6, 7-9, and 10. Headache will be evaluated by administration of a headache questionnaire at day-1, day-7 and day-14.

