#### 4.12. Algorithm

## 5. DUMMY TABLES

Table 4. Number of Cryptococcal meningitis in patients with HIV infection enrolled from individual specialist hospital

Hospital	Number (N)	Percentage (%)
Specialist hospital Waibargi		
Specialist hospital Mingalardon		
Specialist hospital Thakeyta		
Total		

Table 5. Distribution of age among study group of Cryptococcal meningitis in patients with HIV infection

Age (completed years)	Amphotericin B, Flucytosine plus Fluconazole group	
	Number	Percentage
≤20		
21-40		
>40		
Total		

Table 6. Distribution of gender among study group of Cryptococcal meningitis in patients with HIV infection

Gender	Amphotericin B, Flucytosine plus Fluconazole group	
	Number	Percentage
Male		
Female		
Total		

Table 7. Frequency distribution of headache among study group by Numerical rating Scale at day-1, day-7 and day-14

Days	Headache	Amphotericin B, Flucytosine plus Fluconazole group	
		Number	Percentage
day-1	No pain		
	Mild		
	Moderate		
	Severe		
	Intolerable		
Day-7	No pain		
	Mild		
	Moderate		
	Severe		
	Intolerable		
Day-14	No pain		
	Mild		
	Moderate		
	Severe		
	Intolerable		

Table 8. Clinical effectiveness of study group by assessing presence of headache, fever, convulsion, abnormal mental status and death at day-1, day-7 and day-14

Clinical parameters	Amphotericin B, Flucytosine plus Fluconazole group					
	Day 1		Day 7		Day 14	
	N	%	N	%	N	%
Headache						
Fever						
Convulsion						
Abnormal mental status						
Death						

Table 9. Laboratory-defined adverse events of amphotericin B, flucytosine and fluconazole at baseline and day-7 and day-14 by DAIDS grading

Days	DAIDS Grading	Hematological parameters & Biochemical parameters								Total
		Anaemia N (%)	Neutropenia N (%)	Thrombocytopenia N (%)	Elevated ALT level N (%)	Elevated AST level N (%)	Hypokalemia N (%)	Hyper creatinemia N (%)		
Baseline	Grade 1									
	Grade 2									
	Grade 3									
	Grade 4									
Day-7	Grade 1									
	Grade 2									
	Grade 3									
	Grade 4									
Day-14	Grade 1									
	Grade 2									
	Grade 3									
	Grade 4									

Table 10. Proportion of patients with grade 3 and 4 adverse events of hematological parameters at baseline, day-7 and day-14

	Grade 3 and 4 adverse events	Baseline		Day -7		Day -14	

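### The sample size of 27 rests on the 95% precision of two proportions, but the plan reports neither with an interval, does not define headache improvement, and tabulates each day separately

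*Combined protocol and SAP*

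**What the plan says.** **Sizing (section 4.7.1).** The single-proportion precision formula is applied twice with z = 1.96. The safety input is the "Proportion of absence of grade III/IV anaemia in patients with HIV-associated cryptococcal meningitis infection", set at 0.83 with absolute precision 0.14. The effectiveness input is the "Proportion of improvement of headache in patients with HIV-associated cryptococcal meningitis infection after being treated with Amphotericin, Flucytosine plus Fluconazole", set at 0.8 with absolute precision 0.15. Each is given a minimum of 27 patients. Both are described as measured after treatment, with no day named.

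**Headache.** Objective 3 in section 3.2 is "To determine the severity of headache before and after treatment by numerical rating scale". Section 4.10 (3)(i) sets five bands (0, 1-3, 4-6, 7-9 and 10) and says "Headache severity will be categorized according to the number given by patients for their headache". Neither place says what change counts as improvement.

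**Analysis (section 4.9).** "The parameters for clinical effectiveness and laboratory-defined adverse event gradings will be described by number, percentage in treatment group".

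**Outputs (section 5).**
- Table 7: "Frequency distribution of headache among study group by Numerical rating Scale at day-1, day-7 and day-14".
- Table 8: "Clinical effectiveness of study group by assessing presence of headache, fever, convulsion, abnormal mental status and death at day-1, day-7 and day-14".
- Table 10: "Proportion of patients with grade 3 and 4 adverse events of hematological parameters at baseline, day-7 and day-14".

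All three give number and percentage for each day on its own. None has a row for patients improved, or a confidence interval. In the methods, the 95% confidence level appears only as the label on z in section 4.7.1.

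**The concern.** A precision-based sample size says how wide the confidence interval for a stated proportion should be. Here that is the only justification given for 27 patients. Followed as written, the plan never reports the intervals. It also does not yield the headache proportion if improvement means that a patient's own headache became less severe, because separate day totals do not show which patients moved.

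If the definition, day and denominator stay open until the data are in, they can be chosen with the results in view. The headache figure depends heavily on that choice; the anaemia figure depends on it less.

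**Working it through.** **1. The plan's own figure.** n = z² p(1 − p) / d².
- Safety: 1.96² × 0.83 × 0.17 / 0.14² = 27.66.
- Effectiveness: 1.96² × 0.80 × 0.20 / 0.15² = 27.32.

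The stated 27 is each value with the fraction dropped; rounding up gives 28. At n = 27 the half-widths, 1.96 × √(p(1 − p)/27), are 0.142 and 0.151, just over the targets. So the sizing reproduces, and it rests on precision alone.

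**2. Headache: what the day totals can identify.** The counts are assumed: 27 patients, no deaths, bands in the order none / mild / moderate / severe / intolerable. Day 1 is 0/5/10/10/2 and day 14 is 6/9/7/5/0. Both cross-tables below have exactly these totals.

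| Day-1 band | Fewest improved | Most improved |
|---|---|---|
| Mild (5) | 5 stay mild | 5 to none |
| Moderate (10) | 7 stay moderate, 3 to none | 9 to mild, 1 to none |
| Severe (10) | 5 stay severe, 2 to mild, 3 to none | 7 to moderate, 3 stay severe |
| Intolerable (2) | 2 to mild | 2 to severe |
| **In a lower band** | **3 + 5 + 2 = 10 (37%)** | **5 + 10 + 7 + 2 = 24 (89%)** |

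A linear programme over all cross-tables with these totals confirms 10 and 24 as the limits. The low end needs falls of three bands. With no worsening and falls of at most two bands, the limits are 13 (48%) and 24 (89%).

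If improvement means complete resolution, the same totals fix it at 6/27 = 22%, because nobody is pain-free on day 1. With one pain-free patient on day 1 (1/5/9/10/2), resolution is 5 or 6. Section 2.1.5 cites a trial with headache in 98.2% at presentation, so a pain-free patient at day 1 is possible.

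**3. Headache: denominator after deaths.** Table 8 counts deaths, but no rule says whether the dead stay in the day-14 headache denominator. Section 2.1.13 cites 2-week mortality of 9/63; 27 × 9/63 = 3.9, so take 4 deaths and an assumed 19 improved.
- Survivors only: 19/23 = 83%, Wilson 95% interval 63% to 93%.
- All patients, deaths not improved: 19/27 = 70%, Wilson 95% interval 52% to 84%.

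**4. Anaemia.** Freedom from grade 3/4 anaemia on one named day is 100% minus the Table 10 percentage. Only if freedom at both day 7 and day 14 was meant does Table 10 fall short. The sizing rate gives 0.17 × 27 = 4.6 patients affected, so assume 4 at day 7 and 5 at day 14. The number ever affected is between max(4, 5) = 5 and 4 + 5 = 9. That leaves 22 (81%) down to 18 (67%) of 27 never affected.

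**5. The interval that would go unreported.** A result near either target, such as 22/27 = 81%, has a 95% interval of 63% to 92% (Wilson) or 62% to 94% (exact).

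**The case against.** The strongest reply is that this is a descriptive study with no named primary endpoint. Its objectives are to describe parameters at set days, and the tables do that. Objective 3 asks for severity before and after treatment, which Table 7 shows. This stands: a reader might infer that the study cannot meet its stated objectives, and the documents do not support that. The fault is a mismatch between section 4.7.1 and the analysis plan. Within-patient change is one reading of improvement, not one that the plan states.

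On anaemia, fluconazole is the second week of treatment, so day 14 is a natural reading of the sizing text, and Table 10 then gives the proportion directly. A reader might infer that the safety result cannot be recovered from the tables. That is true only if freedom at both visits was meant, which the plan does not say.

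A reader could also compute an interval from a number and percentage. That holds once numerator and denominator are fixed; for headache they are not.

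The counts above are assumed and show what the tables leave open, not an expected error. It is also tempting to infer a large loss of precision from patients too unwell to give a score. The documents do not say how many could not score, and the definition of abnormal mental status includes lethargy and somnolence, so no figure is put on this. Finally, section 4.12 (Algorithm) has no content in the text available; a definition or time point there would narrow the point.

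**Conclusion.** The point holds in this form. The study is sized on the precision of two proportions, and the plan as written reports neither with an interval. Headache improvement has no definition, day or post-death denominator. If it means a within-patient fall in severity, the planned tables cannot yield it: 10 to 24 of 27, or 13 to 24 under the tighter restriction, on one assumed set of totals. The denominator alone moves the illustrative result from 83% to 70%. For anaemia, only the time point and the interval are lacking, unless both visits were meant.

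This is a gap in the analysis plan more than in data collection. The pro forma already records headache band and haemoglobin for each patient at each visit. The correction should be made before results are seen, and it does not alter the sample size.

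**What to change.** 1. Add a day-1 by day-14 cross-table of headache band, with a day-14 column for patients who died or could not be assessed.
2. Before results are seen, state in section 4.9 what counts as improved. One option is a lower band at day 14 than at day 1, among patients with a day-1 score above 0; if resolution was meant, say so. Keep deaths and non-assessable patients in the denominator as not improved, and give assessed survivors as a sensitivity result. Other rules are defensible; what matters is that one is fixed in advance.
3. Name the time point of the anaemia proportion. If it covers both visits, count each patient once.
4. Report both proportions with Wilson or exact 95% confidence intervals.

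**Cost.** One cross-table, two intervals, a few lines in section 4.9, and a tick-box for death or not assessable on the pro forma, which shows no such field. If freedom from anaemia covers both visits, add one per-patient row. No new patients, visits or procedures are needed. The headache percentage may come out lower, because deaths and non-assessable patients count as not improved.

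### The sample size of 27 makes no allowance for early death, and the plan does not say how patients who die enter the day-14 percentages

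*Combined protocol and SAP*

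**What the plan says.** Section 4.7.1 applies the single-proportion precision formula twice.

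- **Safety:** "p = Proportion of absence of grade III/IV anaemia in patients with HIV-associated cryptococcal meningitis infection" after treatment with the three drugs, taken as 0.83, with "d = Absolute precision = 0.14".
- **Effectiveness:** "p = Proportion of improvement of headache in patients with HIV-associated cryptococcal meningitis infection" after the same treatment, taken as 0.8 without a source, with "d = Absolute precision = 0.15".

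Each calculation ends with "n = minimal required sample size = 27", and 27 is adopted with no addition for death, withdrawal or missing results. Section 4.7.2 includes all admissions in the study period, so 27 is a floor and not a cap.

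Sections 4.8 and 4.10 list death among the effectiveness parameters, and Table 8 gives it a row. Section 2.1.13 reports from a cited study: "Mortality was 14% (nine/63) at 2 weeks". Section 4.9 says only that effectiveness parameters and laboratory gradings "will be described by number, percentage in treatment group". No section says whether a patient who dies before an assessment stays in its denominator.

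**The concern.** A patient who has died has no day-14 headache score and no day-14 blood result. The precision calculation treats every enrolled patient as assessable, in a disease where the protocol itself cites appreciable two-week mortality.

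Section 4.7.1 does not name a day, but day 14 is the natural reading. Both proportions are defined after treatment that includes fluconazole, which is given only in the second week (section 4.8; Annex 1, part V). Day 14 is the only scheduled assessment after all three drugs.

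Two things are at stake. The smaller is that the stated precision may be slightly optimistic. The larger is the meaning of the day-14 percentages, which are the study's whole quantitative output. With no rule for deaths, the table layouts allow readings that make patients who died disappear or look well.

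**Working it through.** **Inputs.** From section 4.7.1: z = 1.96; p = 0.83 and d = 0.14 (anaemia-free); p = 0.8 and d = 0.15 (headache improved); n = 27. From section 2.1.13: two-week mortality 9/63 = 14.3%. This last figure is a cited study's result, used here as an assumption, with a range of 10% to 20% around it.

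**1. The plan's own figure.** n = z² p(1 − p)/d².

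- Anaemia: 1.96² × 0.83 × 0.17 / 0.14² = 27.66.
- Headache: 1.96² × 0.8 × 0.2 / 0.15² = 27.32.

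The plan's 27 is reproduced by dropping the fraction; rounding up gives 28. The half-width at n = 27, from 1.96 × √(p(1 − p)/n), is 0.142 and 0.151. The stated precision is met to two decimals, with nothing in reserve.

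**2. Patients alive at day 14 if exactly 27 enrol.** 27 × (1 − 9/63) = 23.1, about 23.

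**3. Half-width with survivors as the denominator.**

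| Assumed loss | Assessable | Anaemia (stated 0.14) | Headache (stated 0.15) |
|---|---|---|---|
| none | 27 | 0.142 | 0.151 |
| 10% | 24 | 0.150 | 0.160 |
| 14.3% | 23 | 0.153 | 0.163 |
| 20% | 22 | 0.157 | 0.167 |

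At 23 patients the widening is about 1.2 to 1.3 percentage points.

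**4. Headache with all 27 kept and death counted as not improved.** The answer depends on what 0.8 means.

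- If 0.8 already counts deaths as failures: 1.96 × √(0.8 × 0.2/27) = 0.151, as stated in the plan.
- If 0.8 applies to survivors only: 0.8 × 23 = 18.4 improved, and 18.4/27 = 68%. The half-width is 1.96 × √(0.68 × 0.32/27) = 0.176. The survivors-only figure would then be 80 − 68 = 12 points higher.

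**5. How the dummy tables treat a death.**

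- Table 7 has five headache categories and none for death, so its day-14 rows cannot add up to all enrolled once someone has died.
- Table 8 counts the presence of headache. If 20% of 23 survivors have headache, that is 4.6 patients: 4.6/23 = 20% of survivors, but 4.6/27 = 17% of all enrolled. Over all enrolled, each death lowers the headache rate, because a patient who died is implicitly headache-free.
- Tables 9 to 11 count graded events and have no row for patients without a result. Divided by all enrolled, they count patients who died as free of grade 3/4 events; divided by survivors, those patients vanish from the table.

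**The case against.** The strongest reply is that 27 is a minimum and all admissions over twelve months are included. More than 27 may well enrol, and the shortfall would then shrink or disappear. That stands. A reader might infer that the stated precision will not be delivered, but the documents support this only if enrolment stops at or near 27. They give no forecast of admissions either way.

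A reader might also take 14% as the protocol's own planning assumption. It is not. It sits in a literature paragraph that runs several studies together, and the text does not make clear which regimen it describes. For one week of amphotericin B plus flucytosine that section gives only a 10-week figure (24.2%). Hence the range above.

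A third tempting inference is that reported improvement will be overstated by 12 points. That needs 0.8 to refer to survivors only, and section 4.7.1 gives 0.8 neither a source nor a definition. If deaths are already failures within 0.8, keeping all 27 returns the stated precision. The dummy tables also have no row for improvement, so that exact figure is not yet a planned output.

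It is also fair that no day is named in section 4.7.1, that a patient who dies after day 7 can still contribute day-7 data, that no hypothesis test depends on one percentage point of half-width, and that Table 8 shows deaths alongside headache. These points limit the size of the precision problem. They do not supply a denominator rule, and higher enrolment would not supply one either.

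**Conclusion.** The concern holds in a limited form. The sample size has no reserve and no allowance for early death. With 27 enrolled, 14% two-week mortality and survivors-only percentages, the half-widths are about 0.153 and 0.163 against 0.14 and 0.15. For assumed losses of 10% to 20% they are 0.150 to 0.157 and 0.160 to 0.167. That alone is minor.

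The undefined day-14 denominator matters more. Its possible effect on headache improvement runs from nothing to about 12 points, depending on what 0.8 means and how deaths are handled. The favourable direction is clearest for headache, and for any event counted over all enrolled. For laboratory events among survivors only, it depends on how often those who died had severe toxicity, which the documents do not say. Overall priority is minor to moderate: the study is descriptive and is not invalidated.

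**What to change.** No extra patients or procedures are needed.

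1. **Section 4.7.1.** State the day-14 precision as about ±0.15 (anaemia) and ±0.16 (headache) for about 23 assessable patients if 27 enrol, and note that it improves if more enrol. Give the mortality figure as an assumption taken from a cited study.
2. **Headache improvement.** Define improvement, since section 4.10 defines only severity categories. Report it at day 14 over all enrolled patients, with death before day 14 counted as not improved, next to the survivors-only figure. Say whether p = 0.8 counts deaths as failures: the half-width is about 0.15 at n = 27 if it does, and the expected result is about 68% with ±0.18 if 0.8 applies to survivors only.
3. **Tables 7 and 8.** Print the denominator at each visit, so that presence of headache is never divided by a total that silently includes patients who have died.
4. **Tables 9 to 11.** Use patients with a result at that visit as the denominator, print it, and show the number who died before the visit.

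The cost is protocol and table wording, and a slightly less favourable stated precision. If the sponsor would rather keep 0.14 and 0.15 among survivors, 27/0.86 = 31.4 and 28/0.86 = 32.6, so about 32 to 33 enrolled would do it; this is optional.
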